2. STUDY DESIGN

2.1 Study Objectives

The objective of the study is to expand the knowledge of safety, performance and effectiveness of the usage of Edwards PASCAL Transcatheter Valve Repair System in the treatment of patients with an insufficient mitral valve.

2.2 Overall Study Design and Plan

This is a post market, prospective and retrospective (where applicable), observational, single-arm, multicenter, registry study of the Edwards PASCAL Transcatheter Valve Repair System for the percutaneous reconstruction of patients with an insufficient mitral valve.

A minimum of 200 patients will be enrolled in the registry at over 10 sites in the Europe.

Patients will be treated per standard of care at their medical facilities and a written informed consent will be obtained to allow the data to be collected. This registry will enroll patients

[REDACTED]

 Edwards	Revision Date: August 22, 2019		Rev	1.0	For Use Only by Affiliates of Edwards Lifesciences	Page 6 of 13
	Title	Statistical Analysis Plan for PASCAL Registry				

under commercial usage and will serve as a mechanism to collect clinical data to further characterize the safety, performance and effectiveness of the PASCAL Transcatheter Valve Repair System.

A description of each study visit and required study procedures is included in the clinical protocol Section 4: Procedures and Methods.

3. OUTCOME MEASURES

3.1 Primary Safety Measures

- Major Adverse Events (MAE) at 30 days. MAEs – composite of all-cause death, Myocardial Infarction, Stroke, Heart Failure Hospitalization, or complication requiring transcatheter or surgical intervention (repeat PASCAL or Mitral Valve Surgery).

3.2 Primary Performance Measure

- MR reduction to $\leq 2+$ at 30 days and 12 months

3.3 Secondary Measures

1. Adverse event assessment (all follow up visits)
2. EQ-5D-5L or KCCQ at baseline, 30 days and 12 months, if available
3. 6MWT at baseline, 30 days, and 12 months, if available
4. NYHA assessment at baseline, 30 days and 12 months, if available

 Edwards	Revision Date: August 22, 2019		Rev	1.0	For Use Only by Affiliates of Edwards Lifesciences	Page 7 of 13
	Title	Statistical Analysis Plan for PASCAL Registry				

4. ANALYSIS POPULATIONS

The analysis cohorts are defined below:

4.1 Intention-to-Treat (ITT) Population

The intention-to-treat (ITT) population includes all enrolled patient.

4.2 Implanted Population

The implanted population is a subset of ITT population and includes all patients in whom the PASCAL Transcatheter Device is implanted.

The implanted population will be the primary analysis population for this study.

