3.3 Number of Planned Patients

All patients treated with the commercially available PASCAL Transcatheter Valve Repair System and who are not part of any ongoing PASCAL pre or post market study, will be asked to participate in this registry. A minimum of 200 patients are expedited to be enrolled in the registry at sites performing transcatheter valve repair where commercialized PASCAL Transcatheter Device is available.

A patient will be considered enrolled in the registry once the patient has signed the ICF and the procedure has begun (defined as PASCAL guide sheath is inserted into the vasculature).

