8.1 Primary Safety Measures

The primary safety measure for this study is a composite endpoint of Major Adverse Events (MAEs) at 30 days. No hypotheses testing will be performed for this endpoint. The composite MAE and each individual MAE will be summarized by counts, percentage and 95% Confidence Interval (CI) of the percentage for the ITT and implanted population.

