8.3 Secondary Measures

Safety Measures

All AEs and SAEs with onset on or after the procedure date (Day 0) will be summarized using type of event by early events (≤ 30 days) and late events (> 30 days). Summaries of incidence rates (counts and percentages) will be prepared, where data is available.

Functional and Quality of Life Measures

Quality of Life (QoL) as measured by EQ-5D and KCCQ, will be scored according to algorithms provided by the vendor. The various summary scores produced by the algorithms will be analyzed as continuous variables. EQ-5D and KCCQ overall summary scores, and their changes from baseline to 30 days and 12 months will be summarized. Patients that are missing a baseline or follow up values will be excluded from the analysis.

 Edwards	Revision Date: August 22, 2019		Rev	1.0	For Use Only by Affiliates of Edwards Lifesciences	Page 13 of 13
	Title	Statistical Analysis Plan for PASCAL Registry				

Count and percentage of patients in each NYHA Class will be summarized. Change from baseline will be presented as a shift from baseline to 30-day and 12-month follow-up. Patients that are missing baseline or follow-up values will be excluded from the paired analysis.

Summary statistics, including mean, median, SD, and sample size, for 6MWT will be presented. Change in 6MWT at 30 days and 12 months over baseline will be summarized. Patients that are missing baseline or follow-up values will be excluded from the paired analysis. Patients unable to perform the walk due to a medical reason will be considered to have walked a distance of 0 m.

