9. ANALYSIS OF SAFETY

9.1 Deaths

The primary cause of death will be summarized descriptively by counts and percentages at 30 days and 1 year. No statistical testing will be performed.

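### The SAP makes implanted patients the primary population for safety too, and assures no all-enrolled table for non-MAE complications, causes of death or events after Day 30

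*SAP*

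**What the plan says.** The SAP defines two sets. Section 4.1: "The intention-to-treat (ITT) population includes all enrolled patient". Section 4.2 takes the subset that "includes all patients in whom the PASCAL Transcatheter Device is implanted" and adds: "The implanted population will be the primary analysis population for this study". That sentence carries no exception for safety.

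Enrolment comes before implantation. Protocol 3.3 and 4.3 count a patient as enrolled once consent is signed and the procedure has begun, "defined as PASCAL guide sheath is inserted into the vasculature". A patient whose attempt ends without a device is therefore enrolled and in the ITT set, but not in the implanted set.

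The safety sections treat population differently:

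- SAP 8.1 (30-day MAE, composite and each component) gives counts, percentages and "95% Confidence Interval (CI) of the percentage for the ITT and implanted population".
- SAP 8.3 (all AEs and SAEs, split at 30 days) says: "Summaries of incidence rates (counts and percentages) will be prepared, where data is available". No population is named.
- SAP 9.1 says: "The primary cause of death will be summarized descriptively by counts and percentages at 30 days and 1 year". No population is named.
- SAP 9.2 only refers back to 8.3.

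**The concern.** Whether a device ends up implanted is decided after exposure to the procedure has begun, and an attempt may be abandoned because of a complication. A safety rate restricted to implanted patients conditions on a post-exposure event. If abandoned attempts have more complications, the restricted rate is too low.

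The rest of the design counts from the start of the procedure. Day 0 is the index procedure, tied to sheath insertion (SAP 5.1.1). Protocol section 6 captures events for every registry patient from the procedure on. The exit criteria in Protocol 3.7 do not list non-implantation, so these patients stay in follow-up. The registry collects their safety data, but outside 30-day MAE the SAP does not commit to tabulating them. Safety is a stated registry objective and one of its two primary measures.

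**Working it through.** The plan states no expected event rate, non-implant rate or precision target, so there is no figure of its own to reproduce. The check has two parts.

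**1. Which population each safety output uses**

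| Output | Population named | Non-implanted patients assured? |
|---|---|---|
| 30-day MAE and its 5 components (SAP 8.1) | ITT and implanted | Yes |
| AEs/SAEs up to and after 30 days (SAP 8.3, 9.2) | None; default from 4.2 is implanted | No |
| Cause of death at 30 days and 1 year (SAP 9.1) | None; default from 4.2 is implanted | No |

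The MAE components (SAP 3.1) are all-cause death, myocardial infarction, stroke, heart failure hospitalization, and complications needing repeat PASCAL or mitral valve surgery. Compared with the event list in Protocol section 6, these fall outside MAE: bleeding, vascular and transseptal complications, other unplanned cardiac or vascular surgery, and new dialysis. For patients without an implant, these events have no assured all-enrolled table. The same is true of causes of death, and of deaths and adverse events after Day 30.

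**2. How large the effect could be**

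Let f be the fraction enrolled but not implanted, pF the event rate in those patients, and pI the rate in implanted patients.

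- All-enrolled rate = f × pF + (1 − f) × pI
- Gap (all-enrolled minus implanted) = f × (pF − pI)
- Share of events missing from an implanted-only table = f × pF / [f × pF + (1 − f) × pI]

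Inputs: N = 200 is the planned minimum (SAP 2.2). The documents give none of f, pF or pI, so the values below are assumptions. The nearest figure is the 96% technical success among 23 compassionate-use patients in Protocol 1.7.1. It matches 22/23 = 95.7%, with an exact 95% CI of about 78% to 99.9%. It is not defined there as an implant rate, so it does not fix f.

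With pF = 25%:

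| f | Not implanted, of 200 | pI | All-enrolled rate | Gap (points) | Share of events missing |
|---|---|---|---|---|---|
| 2% | 4 | 5% | 5.4% | 0.4 | 9% |
| 4% | 8 | 5% | 5.8% | 0.8 | 17% |
| 10% | 20 | 5% | 7.0% | 2.0 | 36% |
| 2% | 4 | 10% | 10.3% | 0.3 | 5% |
| 4% | 8 | 10% | 10.6% | 0.6 | 9% |
| 10% | 20 | 10% | 11.5% | 1.5 | 22% |

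Worked line, f = 4% and pI = 5%: expected events are 8 × 0.25 = 2 without an implant and 192 × 0.05 = 9.6 with one. The all-enrolled rate is 11.6/200 = 5.8%, the gap is 0.04 × (0.25 − 0.05) = 0.8 points, and the missing share is 2/11.6 = 17%.

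If pF = pI the gap is zero. For scale, the exact 95% CI for 10/200 = 5% is 2.4% to 9.0%, so gaps of 0.4 to 2.0 points lie within sampling error. Unlike sampling error, they run towards looking safer whenever pF exceeds pI.

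**The case against.** The strongest reply is that the primary safety measure is already covered. SAP 8.1 reports the composite and every component in both sets, with confidence intervals. There is no hypothesis test, margin or success criterion, so which MAE rate is called primary changes a label and hides no result. This stands, and it rules out a stronger reading: that deaths after failed attempts vanish from the safety report. Suppose 2 of 8 non-implanted and 4 of 192 implanted patients die by Day 30. The ITT row of 8.1 shows 6/200 = 3.0%. Only the cause-of-death table, on the implanted default, would rest on 4/192 = 2.1%. SAP 7.1 also plans a disposition summary and a patient-level listing, and death is an exit reason, so later deaths may be visible there. That listing is not a safety table and does not replace one.

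A second reply is that 8.3 and 9.1 are silent, not restricted. Section 8.3 refers to all AEs and SAEs from Day 0, which could be read as all enrolled patients. This also stands in part: the implanted default is an inference from 4.2. It is the more natural one, because 8.1 names ITT where it is wanted and SAP 6.1 plots Kaplan-Meier results in days from implantation. If both readings are open, the population needs to be stated.

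Third, a reader might take the implanted set to mean successful implants. SAP 4.2 requires only that a device is implanted, so poor MR results, single-leaflet attachment, embolization and reintervention after implantation remain in it.

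Finally, the effect size rests on assumed rates. That is so, and the working says so.

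**Conclusion.** The concern holds within limits. By SAP 4.2 the primary safety result is the one in implanted patients, a set defined by something that happens after exposure starts. Thirty-day MAE and its components, including all-cause death, are still reported for all enrolled patients. The gap lies in 8.3 and 9.1: for patients without an implant, nothing assures a table of non-MAE complications, causes of death, or deaths and adverse events after Day 30.

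The bias is towards looking safer if failed attempts have higher event rates, and absent if they do not. Under the assumed f = 2–10%, pI = 5% and pF = 25%, rates are understated by 0.4 to 2.0 points and 9% to 36% of events are missing from the affected tables. The rate shift is modest against the precision of 200 patients; the share of procedural events left out may not be. The finding about unnamed populations rests on the text alone. Its size rests entirely on the assumed rates.

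**What to change.** - SAP 4.2 and 8.1: make ITT (all enrolled) the primary population for safety, with Implanted as supportive.
- SAP 8.3 (safety measures) and 9.1: add *ITT population; repeated for the Implanted population*. Section 9.2 follows through its reference to 8.3.
- With the disposition summary in 7.1, give the number enrolled but not implanted and the reasons, so that readers can see f.

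No new data are needed, because Protocol section 6 already captures events for all registry patients. The cost is a few SAP sentences, one repeat of existing tables, and a headline safety figure that may be slightly less favourable.

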5. DEFINITIONS

5.1 Analysis Dates

5.1.1. Reference Start Date and Day 0

The reference start date is defined to be the date of the index procedure. The index procedure is defined as the time of the PASCAL guide sheath is inserted into the vasculature. If a patient has multiple procedure forms, we will present information on the procedure with the first date when the site has indicated that the PASCAL guide sheath is inserted into the vasculature. If no form has this indicated, then the procedure information corresponding to the date of the first procedure will be used.

The reference start date is considered to be Day 0.

 Edwards	Revision Date: August 22, 2019		Rev	1.0	For Use Only by Affiliates of Edwards Lifesciences	Page 8 of 13
	Title	Statistical Analysis Plan for PASCAL Registry				

5.1.2. Last Participation Date

The last participation date is defined as the latest date assessed with any available information concerning the patient (e.g., latest date out of: baseline assessment, procedure, discharge, follow-up visit, unscheduled visit, echo data, laboratory tests collection, study exit when exit reason is not lost to follow-up, and adverse event occurrence).

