3.7 Registry Exit Criteria and Procedures

The reason for exit from the registry will be documented on the appropriate case report forms and in the medical records for each patient who exits the registry.

Patients may exit the registry for any of the following reasons:

- Completion per Protocol
- Withdrawal
 - Patient Withdrawal: The patient may voluntarily withdraw from the registry at any time, without penalty or loss of benefits to which they are otherwise entitled.
 - Physician Withdrawal: The Investigator also has the right to withdraw a patient if s/he feels it is in the best interest of the patient to do so.
 - Sponsore Withdrawal: The Sponsor may prematurely terminate the Registry.
- Death
- Device Reintervention or Explant
 - Patients who have a surgical reintervention where the device is explanted will be followed for 30 days post-reintervention or until resolution of any adverse events related to the procedure and then exited from the registry. Patients that have a percutaneous or surgical reintervention where the device remains in place will continue to be followed for the duration of the registry.

- Lost to Follow-up
 - If a patient cannot be reached for a follow-up visit, the Investigator will document the contact efforts made to the patient and/or effort to obtain hospital records in the appropriate electronic case report form. If the patient cannot be reached in any way, or misses a visit, the patient will be considered “unable to contact” for that time interval. After three (3) documented unsuccessful attempts to make contact prove unsuccessful, a certified letter will be sent to the patient’s residence. If there is no response after the certified letter is sent, the patient will be considered “lost to follow-up”.
 - For patients who are lost-to-follow-up or withdraw early, Edwards may request the site to search death registries as available or applicable per GDPR requirements and may request the site to obtain the death certificate, if applicable.

In all cases of withdrawal (as described above), no additional data will be collected.

All data collected up until the time of withdrawal will be analyzed and will be retained for the duration of the registry.

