4.5 Data Collected

Routine clinical (such as Medical History, Risk Factors, Medication, Clinical Status, Procedure Information and Safety data) and echocardiographic data available from clinical records will be collected for the following time points:

- Baseline: pre-procedural data
- Procedural data: data collected as part of the procedure
- Discharge data: data collected prior to discharge from hospital
- 30 day visit: visit performed between discharge and up to 2 months post procedure
- 1 year follow up: visit performed between 10 months and 14 months post procedure

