4.7 Registry Termination and Close-Out

The investigator will be notified in writing upon termination/conclusion of the registry. The sponsor retains the right to suspend or terminate this registry at any time.

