5.1.3. Last Participation Day

Last Participation Day = Last Participation Date – Reference Start Date

Note: Last Participation Day is used as the censor day for Kaplan-Meier analysis.

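### SAP 5.1.2 lets a study exit date set the Kaplan-Meier censor day without requiring that the patient's status was known on that date, so administrative exits can lower the late event rates

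*SAP*

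**What the plan says.** SAP 5.1.2 defines the last participation date as "the latest date assessed with any available information concerning the patient" and then gives examples of qualifying dates. One of them is "study exit when exit reason is not lost to follow-up". SAP 5.1.3 adds: "Last Participation Day is used as the censor day for Kaplan-Meier analysis".

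Protocol 3.7 lists the exit reasons: completion, withdrawal by the patient, the physician or the sponsor, death, reintervention or explant, and loss to follow-up. Under sponsor withdrawal it says "The Sponsor may prematurely terminate the Registry", and Protocol 4.7 repeats the right: "The sponsor retains the right to suspend or terminate this registry at any time". For every type of withdrawal, Protocol 3.7 states: "In all cases of withdrawal (as described above), no additional data will be collected".

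In Protocol 4.5 the 30-day visit may fall at any time from discharge to 2 months. The next and last time point is "1 year follow up: visit performed between 10 months and 14 months post procedure".

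SAP 6.1 provides for Kaplan-Meier estimates and plots of time-to-event variables. SAP 6.2 relies on Kaplan-Meier censoring to deal with withdrawal and loss to follow-up.

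**The concern.** A censor day should be the last day on which the patient was known to be event-free. By leaving out the exit date of lost patients, the SAP recognises that an exit date need not be such a day. It makes this exception for one exit reason only. A termination date is the sponsor's decision date and says nothing by itself about the patient. Neither document defines the exit date or asks for a contact or a record check on it.

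If an exit is dated after the last information, the patient stays in the risk set in between and cannot contribute an event. The denominator is too large and the estimated event rate too low, which flatters the device. No contact is scheduled between month 2 and month 10, so the gap can be long. Sponsor termination is listed as a withdrawal, after which no more data are collected, so a gap left at exit would not be filled later.

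At stake are any Kaplan-Meier estimates and plots beyond Day 30, for example of death, heart failure readmission, reintervention, stroke or myocardial infarction.

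**Working it through.** The plan states no event rate, no share of administrative exits and no power calculation, so there is no figure of its own to reproduce. What follows is an illustration.

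**Inputs**
- One-year risk R(365) = 26.2%. This is the annual mortality that Protocol 1.2 cites for conservatively treated patients, used only as an example. Risks of 10% and 34% are also run.
- Share f of patients exited administratively: 10%, 20%, 30% (assumed).
- Last information at Day 30, exit dated Day 365, no event capture in between (assumed).
- Constant hazard, and exits unrelated to risk (assumed).

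**Step 1: risk by Day 30.** S(30) = (1 − 0.262)^(30/365) = 0.738^0.0822 = 0.9753, so R(30) = 2.47%.

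**Step 2: censoring at the exit date.** After Day 30 the risk set holds (1 − f)·S(t) observed patients and f·S(30) unobserved ones, and only the first group can show events. Integrating the diluted hazard gives

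reported risk = (1 − f)·R(365) + f·R(30)

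- f = 10%: 0.9 × 26.2 + 0.1 × 2.47 = 23.8%
- f = 20%: 0.8 × 26.2 + 0.2 × 2.47 = 21.5%
- f = 30%: 0.7 × 26.2 + 0.3 × 2.47 = 19.1%

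The relative understatement is f × (1 − 2.47/26.2), about 0.9 × f.

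**Step 3: other risks, same formula**

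| True one-year risk | f = 10% | f = 20% | f = 30% |
|---|---|---|---|
| 10% | 9.1% | 8.2% | 7.3% |
| 26.2% | 23.8% | 21.5% | 19.1% |
| 34% | 30.9% | 27.9% | 24.8% |

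**Step 4: earlier exit date.** With exit at Day 200 and f = 20%, S(200) = 0.738^(200/365) = 0.8467. Reported survival is (0.8 × 0.8467 + 0.2 × 0.9753) × 0.738/0.8467 = 0.760, a risk of 24.0%.

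**Step 5: simulation check.** With 200 patients, 2,000 runs and a true risk of 26.2%, exit-date censoring gave 23.8%, 21.4% and 19.1%. Censoring at the last information gave 26.1%, 26.2% and 26.2%.

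**Step 6: the opposite error.** Suppose every event does reach the site through records, but event-free patients in share f are cut back to Day 30. The risk set after Day 30 is then S(t) − f·S(365), and

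reported risk = 1 − S(30)·(1 − f)·S(365) / [S(30) − f·S(365)]

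- f = 10%: 1 − 0.9753 × 0.9 × 0.738 / (0.9753 − 0.0738) = 28.1%
- f = 20%: 1 − 0.9753 × 0.8 × 0.738 / (0.9753 − 0.1476) = 30.4%
- f = 30%: 1 − 0.9753 × 0.7 × 0.738 / (0.9753 − 0.2214) = 33.2%

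This error is of the same order with the sign reversed. The remedy therefore cannot simply be to censor at the last visit.

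**The case against.** The case on the other side has four parts.

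*The definition already requires information.* The opening words of SAP 5.1.2 ask for a date with information about the patient, and the list only gives examples. A bare administrative date arguably does not qualify. This shows the intent. But the list names study exit with a single exception, and a programmer following it would use a termination date. The wording should match the intent.

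*Events are captured until participation ends.* Protocol 6 says so, and Protocol 4.5 and 4.6 draw on routine records, including an effort to obtain outside ones. A site that reviews records at exit does observe the interval. This stands, so a reader who infers that administratively exited patients always carry unobserved months goes too far. Still, data are collected as available, most late events are listed under follow-up visits, and no review at exit is required.

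*Closure without a 1-year visit.* A reader might infer that such patients are routinely closed as completed and gain event-free time. The documents do not say this. Under Protocol 3.7 a missed visit makes the patient uncontactable for that interval. After three failed attempts and an unanswered certified letter the patient is lost to follow-up, and SAP 5.1.2 leaves that exit date out. The route exists only if a site codes the exit otherwise.

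*Reach.* SAP 8.1, 8.3 and 9.1 report 30-day MAE, early and late adverse events and causes of death as counts and percentages. No late Kaplan-Meier endpoint is named, and no hypothesis is tested. This stands. SAP 6.2 does link Kaplan-Meier censoring to the primary and secondary measures, so late Kaplan-Meier output under SAP 6.1 and 6.2 is the exposure.

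**Conclusion.** The point holds as a gap in the rule, not as a demonstrated error in the results. As written, SAP 5.1.2 can carry a patient in the risk set past the last information whenever the exit is administrative and dated later. Sponsor termination is the route that the documents support, and it is a reserved right, not a planned event. For exits such as death or the patient's own withdrawal, the date is normally sound.

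The direction is clear: late Kaplan-Meier event rates would be too low. The size is unknown. The fall from 26.2% to between 23.8% and 19.1% rests on assumed shares of 10% to 30%, a constant hazard, no information after Day 30 and exit at Day 365. An earlier exit date shrinks it, and known status at exit removes it. A reader might infer that the primary safety result is biased. The documents do not support that, because SAP 8.1 reports it as a 30-day percentage.

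The correction is worth making before any late curves are produced.

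**What to change.** In SAP 5.1.2, replace the exit item with: *study exit date only when the patient's status (vital status and events) was confirmed through that date by contact or record review; otherwise the last date through which status was documented by contact or record review, whatever the exit reason.*

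Record that status date on the exit eCRF. A rule based on status avoids sorting exit reasons one by one. Counting a documented record review as known status holds patients with and without events to the same standard, which guards against the upward bias in Step 6 of the working.

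The cost is one SAP sentence, one condition in the derivation program and one extra eCRF date. Follow-up becomes slightly shorter and late confidence limits slightly wider.
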